4.7 * EXPEDITED REVIEW CATEGORIES: (REQUIRED) If you think this study qualifies for expedited review, select the regulatory categories that the research falls under: (check all that apply)

- Category 1: Research using approved drugs or devices being used for their approved indications
- Category 2: Collection of blood samples by finger stick, heel stick, ear stick, or venipuncture in certain populations and within certain amounts
- Category 3: Prospective collection of biological specimens for research purposes by noninvasive means (e.g. buccal swabs, urine, hair and nail clippings, etc.)
- Category 4: Collection of data through noninvasive, routine clinical procedures (e.g. physical sensors such as pulse oximeters, MRI, EKG, EEG, ultrasound, moderate exercise testing, etc. - no sedation, general anesthesia, x-rays or microwaves)
- Category 5: Research involving materials (data, documents, records, or specimens) that have been or will be collected solely for nonresearch purposes
- Category 6: Collection of data from voice, video, digital, or image recordings made for research purposes
- Category 7: Research on individual or group characteristics or behavior or research employing survey, interview, oral history, focus group, program evaluation, human factor evaluation, or quality assurance methodologies

* Does the collection of blood samples meet requirements outlined by HHS Office for Human Research Protections for **Expedited Review Research Category 2: (REQUIRED)**

- For healthy, nonpregnant adults who weigh at least 110 pounds the amounts drawn may not exceed 550 ml in an 8 week period and collection may not occur more frequently than 2 times per week;
- From other adults and children, considering the age, weight, and health of the subjects, the collection procedure, the amount of blood to be collected, and the frequency with which it will be collected, the amount drawn may not exceed the lesser of 50 ml or 3 ml per kg in an 8 week period and collection may not occur more frequently than 2 times per week

- Yes No

4.9 * DATA/SPECIMEN ANALYSIS ONLY: (REQUIRED) Does this study ONLY involve records review and /or biospecimen analysis (do not check 'Yes' if this is a registry, research or recruitment database, or biospecimen repository):

Yes No

4.10 * CLINICAL TRIAL: (REQUIRED)

Is this a clinical trial:

According to The World Health Organization (WHO) and the International Committee of Medical Journal Editors (ICMJE) a clinical trial is:

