2) Participants will provide a sample for genetic testing. Subjects will have a blood test at UCSF or go to their physician to provide us with a blood sample. A saliva sample that can be obtained with a kit is an alternative procedure if a subject does not wish to have venepuncture. A buccal swab obtained with a kit is also an alternative to venepuncture. The blood, saliva, or buccal swab samples will be used to obtain the genetic material (DNA) for laboratory testing. Repeat studies may be needed in some cases and subjects may be asked to give another blood sample in the future, but may choose not to donate the second sample. About two ounces of blood will be drawn from adults (5-7 teaspoons; around 5 ml) and one ounce (3-4 teaspoons; around 2-3 ml) from children depending on weight. The maximum collected for each study subject will be less than 3 ml/kg in neonates and children and less than 20 ml in adults. The blood will be taken by needle in a similar manner to other blood samples. The blood or saliva samples will be sent to the testing laboratory with patient identifiers, such as name, date of birth and medical record number, and will be stored in a locked laboratory for the entire study.

3) The DNA sample from the patient will undergo whole exome sequencing (WES). WES entails searching for genetic changes that can lead to or predispose to intellectual disability, multiple congenital anomalies, seizures and other neurological findings such as a movement disorder, metabolic condition, or a neurodegenerative condition. After the patient's sample has been tested, we may also test parental samples to better understand the child's genetic information. Parental testing may be exome sequencing or more targeted testing of individual genetic variants identified in the child. Patient and family history and examination data (for example, pedigrees) will be collected as per standard clinical practice. These data may include information on family members who are not enrolled in the study as per standard clinical practice. We may also obtain photographs of some affected individuals as per standard clinical practice. These photographs will be obtained with the permission of the individuals concerned. Use of recognizable photographs (eyes showing) will require written permission from the participant(s) or guardian concerned using a separate consent form that is not part of the study.

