Samples obtained for WES will be collected by either blood draw or saliva sample for the pediatric patients (study #17-22504) and all parent participants. We may also use DNA derived from a specimen that was previously obtained for other diagnostic purposes, including microarray analysis. For participants undergoing WES in the prenatal study (study #17-22420), DNA samples submitted for WES will be derived from a previously obtained specimen -- an entry criterion for the prenatal study is that all participants will have previously undergone prenatal genetic diagnosis by established methods of karyotyping and/or chromosomal microarray analysis.

No invasive procedures other than a simple blood draw are connected with the use of the WES test in either study.

The testing does not introduce energy into study participants. All imaging performed for inclusion criteria in the prenatal arm is clinically indicated and will have been completed prior to enrollment by the patient's clinical provider(s). Magnetic resonance imaging (MRI) or computerized tomography (CT) scan will not be used for diagnosis of a fetal anomaly as part of this study.

To mitigate the risk for a false positive result from the WES pipeline, all sequence variants with clinical relevance that will be reported will be confirmed by Sanger sequencing, a test that is the current laboratory "gold standard" for variant detection. We anticipate that WES in both the pediatric and prenatal studies will yield an underlying genetic cause in approximately 30-40% of patients tested. The majority of study participants will therefore have non-informative test results. When appropriate, Sanger sequencing may be applied to investigate genes in which there is high clinical suspicion for sequence variants that may have been missed by WES.

Any necessary language for labeling will be applied.

Attach any documentation you have from the manufacturer and/or FDA to support this determination.

9.5 LIST THE DEVICES: List the medical devices or in vitro diagnostics to be studied or used. In the device details screen you will be asked questions such as:

- Whether the device is FDA approved or investigational
- Medicare device category
- If the device will be provided at no cost
- If an IDE is necessary, the IDE number, and who holds the IDE
- Risk category of the device
- FDA status of the device

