14.0 Risks and Benefits

14.1 RESEARCH-RELATED RISKS: Check if your study involves any of these specific research-related risks to participants that may need to be disclosed in the consent form:

- For interventional studies, risk that the regimen may be more harmful or less effective than other available interventions
- Risks associated with radiation exposure for imaging studies specifically for research purposes
- Risks associated with the administration of contrast agent for imaging studies
- Risks associated with withholding of treatment or discontinuation of current treatment (e.g., washout period is required by the study protocol)
- For randomized, placebo-controlled trials, possible temporary or permanent health consequences from the deprivation of effective therapies during the placebo administration period
- For studies involving a sham surgical procedure, the risk that participants may experience increased morbidity without the possibility of benefit
- Risks associated with modification or extension of a surgical procedure primarily for research purposes (e.g. risks associated with prolonging anesthesia, time in the operating room, etc.)
- Risk of pain or physical discomfort caused by the research intervention
- Possible personal discomfort due to sensitive topics (stress, embarrassment, trauma)

14.2 * RISKS: Describe any anticipated risks and discomforts not listed above: (REQUIRED)

The physical risks from blood drawing or obtaining saliva are very small. There is usually a short-lived pain with a needle stick for a blood draw and there may be bruises at the place of the needle stick. There is also a very small chance of infection, excess bleeding or fainting (feeling lightheaded) from blood drawing. The risk involved will not be any different from that experienced during any clinical blood test. The amount of blood taken will not be enough to cause anemia. Saliva sample collection and buccal swab collection are non-invasive and don't pose any significant risks.

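### The blood volumes in Protocol section 7.9 are given in three units that do not agree, and both adult household figures exceed the protocol's own 20 ml limit

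*Protocol*

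**What the plan says.** Item 2 of the Procedures list in Protocol section 7.9 states the volume of a draw: "About two ounces of blood will be drawn from adults (5-7 teaspoons; around 5 ml) and one ounce (3-4 teaspoons; around 2-3 ml" for children, adding that the child amount depends on weight. Shortly afterwards the same paragraph sets a ceiling: "The maximum collected for each study subject will be less than 3 ml/kg in neonates and children and less than 20 ml in adults". Just before the volumes it allows for a second draw: "Repeat studies may be needed in some cases and subjects may be asked to give another blood sample in the future". The subject may decline that second sample.

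Other text bears on the consequence:

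- Section 7.9 offers saliva, and also says "A buccal swab obtained with a kit is also an alternative to venepuncture".
- Section 9.4 says "We may also use DNA derived from a specimen that was previously obtained for other diagnostic purposes, including microarray analysis".
- Section 14.2 says "The amount of blood taken will not be enough to cause anemia".
- The expedited-review text in section 4.7 prints a limit for children, and for adults outside its healthy, nonpregnant, at least 110-pound group: "the amount drawn may not exceed the lesser of 50 ml or 3 ml per kg in an 8 week period".

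Section 8.1 asks for the amount of blood, but the answer gives no volume. Item 2 is therefore the only place in the available text that states a draw volume for this study.

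**The concern.** The brackets present the ounce, teaspoon and millilitre figures as one quantity in three units. A reader who takes the ounce figure would draw roughly ten times or more what a reader of the millilitre figure would draw. In adults, the two household figures also appear to break the limit given in the same paragraph.

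The instruction reaches many people. Section 10.1 plans up to 1700 parents or other family members, and section 10.7 admits probands up to age 25. Section 7.9 plans 80 patients from intensive care units, including neonatal units. It also lets subjects have blood drawn by their own physician, so the person drawing may be outside the study team and needs one clear number. What is at stake is a clear and safe procedure; no estimate or test depends on it.

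**Working it through.** **Inputs from section 7.9, item 2.** Adult draw: 2 oz, 5-7 tsp, about 5 ml. Child draw: 1 oz, 3-4 tsp, about 2-3 ml. Maxima per subject: less than 20 ml in adults, less than 3 ml/kg in neonates and children.

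**Assumed conversions.** The documents give none, so US units are used: 1 fl oz = 29.57 ml = 6 tsp, and 1 tsp = 4.93 ml.

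**Step 1: do the units agree?** Volume = count × ml per unit.

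| One draw | Ounces | Teaspoons | Stated ml |
|---|---|---|---|
| Adult | 2 × 29.57 = 59.1 ml | 5 × 4.93 to 7 × 4.93 = 24.6-34.5 ml | 5 ml |
| Child | 1 × 29.57 = 29.6 ml | 3 × 4.93 to 4 × 4.93 = 14.8-19.7 ml | 2-3 ml |

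The plan's stated equivalence cannot be reproduced. For adults the ounce figure is 59.1/5 = 11.8 times the millilitre figure. For children it is 29.6/3 = 9.9 to 29.6/2 = 14.8 times. The household units also disagree with each other: two ounces is 12 teaspoons, not 5-7, and one ounce is 6, not 3-4.

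**Step 2: adult draw against the 20 ml maximum.**

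- Ounces: 59.1/20 = 2.96 times.
- Teaspoons: 24.6/20 = 1.23 to 34.5/20 = 1.73 times.
- Millilitres: 5/20 = 0.25 times.

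Only the millilitre figure fits.

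**Step 3: child draw against 3 ml/kg.** The text scales the child amount by weight, so this step shows only what would follow if it were not scaled. Weight at which the volume reaches the limit = volume / 3.

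- One ounce: 29.6/3 = 9.9 kg.
- 3-4 teaspoons: 14.8/3 = 4.9 kg to 19.7/3 = 6.6 kg.
- 2-3 ml: 2/3 = 0.7 kg to 3/3 = 1.0 kg.

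Above those weights a single draw fits.

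**Step 4: if a repeat sample is taken and counts towards the maximum.**

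- Adults: 118 ml, 49-69 ml or 10 ml. Only 10 ml is below 20 ml.
- Children, unscaled: 59.1 ml reaches 3 ml/kg at 19.7 kg, 29.6-39.4 ml at 9.9-13.1 kg, and 4-6 ml at 1.3-2.0 kg.

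**Step 5: does the choice of unit matter?**

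- Imperial ounces (28.4 ml) give 56.8 ml for the adult draw, 2.84 times the maximum.
- Metric teaspoons (5 ml) give 25-35 ml, and imperial teaspoons (5.92 ml) give 29.6-41.4 ml.
- Only the obsolete fluid-dram teaspoon (3.55-3.70 ml) brings the low end, 5 tsp, under 20 ml (17.8-18.5 ml). At 7 tsp it is still 24.9-25.9 ml, and two ounces exceeds the limit regardless.

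**The case against.** The best defence is that the paragraph limits itself. The volumes are approximate, the child amount is tied to weight, and an explicit ceiling follows. Only the millilitre figure is compatible with the adult ceiling, so a careful reader can recover the intended volume. This stands, and it is why the consequence is small. It does not make the figures equal, and approximation cannot cover a roughly twelve-fold gap.

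The child-weight thresholds assume unscaled volumes, which the text does not intend. That also stands: they describe a condition and do not show that the child limit is broken. The conflict with a limit is shown for adults only.

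A maximum set per subject is most naturally read as covering every draw, including an optional repeat. That is fair. The text does not say so outright, however, and a few added words would settle it.

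Saliva, a buccal swab or an earlier specimen can replace a new blood draw, and the protocol says the volume will not cause anemia. These points lower the chance of harm but do not correct the sentence. The 3 ml/kg limit in section 4.7 is form text, and the available copy does not show which boxes were ticked, so it is context only.

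**Conclusion.** The concern holds and is minor. The three units disagree for adults (about 59, 25-35 and 5 ml) and for children (about 30, 15-20 and 2-3 ml). Both adult household figures exceed the protocol's own maximum, by about 3 times and 1.2-1.7 times. This rests on standard conversions and holds in US, metric or imperial units. No other available text gives a volume that reconciles the figures. The error most likely lies in the household units, since 5 ml is the only adult figure below 20 ml; the investigators need to confirm that. Over-drawing is unlikely, and the design, endpoints and analysis are unaffected.

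**What to change.** In section 7.9, item 2:

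- Delete the ounce and teaspoon figures.
- State each draw once, in millilitres: about 5 ml in adults and 2-3 ml in children, less in the smallest neonates as needed, once the investigators confirm these volumes.
- Keep the two maxima and add that they cover all draws from a subject, including repeat samples.
- Check that any blood volume in the consent wording matches. The consent pages were not available for this review, so no mismatch is claimed.

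The cost is a wording edit to two sentences and the consent check. Nothing in the design or analysis changes.

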The UCSF Fresno/Community Medical Center, one of our study sites, will be enrolling patients starting in January 2020 (their own IRB was recently approved). Three of their team members will be adding data into our Redcap database directly and will therefore have access to our study identifiers. We were unable to add them to the personnel section of the study application because they are not UCSF employees, so we are adding them here as per [name]'s instructions. They team members are

[name], a study coordinator, [contact]; [name], a genetic counselor, [contact]; and [name], a genetic counselor, [contact]; [name], a genetic counselor, [contact]

7.11 INSTRUMENTS: List all questionnaires, surveys, interview, or focus group guides that will be used for this study:

We will also analyze and describe clinical interactions and experiences across prenatal and pediatric clinic settings in order to understand context and document patient-provider

interactions. These activities are part of research and are not part of clinical care. Points 1-3 below (the video recordings of clinical interactions, ethnographic observations and interviews are covered under a separate IRB protocol, 17-23118). Specifically, we will do the following:

1. Conduct detailed, ethnographic observations in each clinical setting to elucidate the full contextual experience of families offered sequencing for a potential genetic disorder identified during pregnancy (the prenatal context) or during the care of their affected infant or child (the pediatric context).
2. Follow 60 families (1/3 prenatal) who accept sequencing and conduct in-depth interviews at two time points, targeting a sample constructed to include ancestral diversity (ascertained by self-reported race/ethnicity) and social/economic status (ascertained by insurance coverage). Physicians and genetic counselors will also video record key clinical interactions. Using the constant comparative method, we will compare and contrast the experience of families. Interviews and analysis of videos will elucidate strengths and limitations of communication, revealing how families—including those from diverse, underserved backgrounds—understand genomic sequencing, its potential outcomes, and its consequences.
3. Using semi-structured interviews, assess the reasoning and experience of 60 families who are offered but refuse sequencing, including the potential impact of economic and access issues.
4. Based on data gathered via the ethnography and the initial interviews, develop (in collaboration with the full P³EGS team and with colleagues across the CSER2 “outcomes and measures” committee) and administer a utility assessment survey tool to the full sample of 800 families sequenced. Here we define utility to include both the parents’ understanding of clinical usefulness as well as their personal views about the value and burden of sequencing.
5. In addition to the utility assessment tool, we will also administer surveys at baseline, return of results, and follow-up meant to provide data about patient demographics, information seeking habits, secondary finding preferences, quality of life, understanding of test results, satisfaction, etc. (see attached surveys). These surveys have been recommended for harmonization by the larger CSER2 consortium. These surveys will be administered in person, over the phone, or via mail or email.
6. We will also contact the providers who referred patients to the study via email and ask if they are willing to complete a provider survey meant to provide information about their experience and comfort level with genetics (this will be done once) as well as assessing their perception of the clinical utility of exome sequencing for the patient(s) they referred (this will be done twice for each patient, once after the patient's return of results appointment and once after their 5-7 month follow-up visit).
7. We will contact executives, administrators, managers or clinicians at UCSF via email to ask if they are willing to complete a survey about organizational readiness to change (ORCA). This survey will be administered once via Redcap or on paper and will not involve any personal identifiers. The goal of the survey is to learn more about their views on the potential for implementation of clinical sequencing in healthcare systems and communities. The de-identified data will be pooled by the University of Washington to include data from the rest of the CSER2 consortium.

Attach any unpublished instruments in the 'Other Study Documents' section of the Initial Review Submission Packet form after completing the study application. Published instruments should NOT be attached.

7.12 * BIOSPECIMEN COLLECTION: Are you drawing any blood or collecting other biosamples (e.g. tissue, buccal swabs, urine, saliva, hair, etc.) for analysis under this protocol and/or storage for future research: (REQUIRED)

Yes No

* Could this study generate genetic data that may be broadly shared (e.g., submitted to NIH in compliance with **Genomic Data Sharing (GDS)/Genome-Wide Association Studies (GWAS)** requirements): **(REQUIRED)**

Yes No

Please make sure your consent form includes the recommended genomic data sharing language.

7.13 STATISTICAL METHODS: Briefly summarize the methods and types of analyses that will be performed:

This study will involve DNA collection from patients with intellectual disability, metabolic disease, encephalopathy, seizures, birth defects and multiple congenital anomaly syndromes and we do not anticipate the enrollment of sufficient patients to justify statistical methods of data analysis. However, statistical analyses relating to genetic investigations will be performed according to standard methods.

7.14 REFERENCES: List only the 5-10 most relevant references (a separate bibliography can be attached for reference purposes if this study involves novel approaches, agents, or an emerging technology that the IRB may not be familiar with):

See attached bibliography.

8.0 Biospecimen Collection and/or Bank Administration

8.1 * TYPE OF SPECIMENS (check all that apply): (REQUIRED)

- Blood (provide amount below)
- Tissue (describe below)
- Other type of biospecimen, such as sputum, cerebrospinal fluid, buccal swabs, etc. (describe below)
- Existing/archival materials (name source below)

Briefly describe the types of biospecimens that will be collected. Provide the amount of blood, if applicable. For leftover/existing/archival material, identify the source:

We will collect venous blood from subjects who consent. In subjects who refuse venipuncture but who agree to a saliva sample, we will obtain a saliva sample or buccal swab using a commercial kit.

8.3 * SPECIMENS ARE: (check all that apply): (REQUIRED)

- Leftover specimens from a clinical diagnostic or therapeutic procedure
- Specimens collected for research purposes only (including extra samples taken during a clinical procedure)
- Other

8.4 * FUTURE SPECIMEN USE: Will any specimens or portions of specimens be retained after the study is over for possible use in future research studies: (REQUIRED)

Yes No

8.5 * SPECIMEN BANKING - CONSENT METHOD: Consent for retaining specimens for future research studies will be obtained via (check all that apply): (REQUIRED)

- Specimen section within a main research study consent form
- Separate specimen consent form
- UCSF surgical consent form with tissue donation brochure

8.6 * SPECIMEN DESTINATION: Indicate where specimens will ultimately be stored: (REQUIRED)

Outside Entities: Indicate where specimens will be sent if they will not remain at UCSF (choose at least one; check all that apply):

- Cooperative group bank
- NIH
- Other university or collaborator
- Industry sponsor
- Other
- N/A - all specimens will remain at UCSF

Internal Storage: If specimens will remain at UCSF, in what kind of facility will they reside (choose at least one; check all that apply):

- UCSF repository/bank being established under this protocol
- Existing UCSF specimen repository/bank with IRB approval
- National cooperative group bank housed at UCSF
- Other location at UCSF (please describe)
- N/A - no specimens will be retained at UCSF facilities

Please provide the name of the department, the program, and the physical location where the specimens will be housed. If the specimens will be stored in an already established bank, provide the name of the bank and its iRIS approval number.:

Genomic Medicine Laboratory (GML) at UCSF

8.8 * CLINICAL FOLLOW-UP DATA: Will clinical follow-up data be linked to specimens (i.e., will medical record information continue to be abstracted after the specimen is collected): (REQUIRED)

Yes No

Provide duration of follow-up or 'indefinitely':

the duration of the study

8.9 * UCSF-BANKED SPECIMENS - LINKING AND SHARING OF IDENTIFIERS: (REQUIRED)

- Samples are completely de-identified before being added to the bank/repository. There is no way to link the specimens back to the subjects.
- Samples are coded and researchers are able to link the specimens to specific subjects.
- Samples are stored with direct identifiers in the repository.

Explain under what circumstances identifiers may be released with specimens or say 'None' if identifiers will **NEVER** be released with specimens:

Samples will not be sent with identifiers for future research.

8.10 UCSF-BANKED SPECIMENS – IDENTIFIERS: List the identifiers that will be collected, stored, or linked with the specimens:

Name

- Date of birth
- Social Security number
- Medical record number
- Address
- Phone number
- Email address
- Other dates (dates of surgery, visit dates)

8.11 DISTRIBUTION: Specimens banked at UCSF may be made available to (check all that apply):

- UCSF researchers
- Non-UCSF researchers
- Industry
- None of the above - specimens will be retained and used within our own research program

8.12 UTILIZATION REVIEW: Is there a formal utilization review process for distribution of specimens:

Yes No

